6.1 Inclusion and Exclusion Criteria

6.1.1 Inclusion Criteria

All participants must meet the following criteria to be included into the study:

Inclusion Criteria

Participant Characteristics

- 1 Males or females between age 60 and 85 years, inclusive, at time of consent.
- Have a dedicated partner/caregiver informant who is in the company of the participant at least 12 hours a week, who can accompany them to scheduled visits, and who is able to provide accurate reporting upon the behavioral, cognitive and functional abilities of the participant. Additionally, the study partner (or LAR or caregiver, if different) must be willing and able to administer the treatment injections. If a study partner must withdrawal from study participation, a replacement study partner may be allowed, at the investigators discretion. The replacement study partner, would need to agree to and sign a separate informed consent on the first visit that he/she accompanies the participant to participate.
- 3 Be physically able to participate by medical history, clinical exam, and other testing, with adequate visual acuity and auditory discrimination.
- Be willing / able to provide written informed consent or assent. If assent is provided, consent must be provided by a legally authorized representative (LAR) or proxy decision maker, who may or may not be the dedicated study partner / caregiver. Documentation of LAR or proxy decision maker status will follow local laws and regulations.

Note: Individuals utilizing a proxy decision maker will not be able to participate in optional sub-studies as a proxy decision maker cannot provide consent for optional non-therapeutic interventions.

Must reside within a proximity of the study site that will not preclude their regularly-scheduled participation in the trial, as well as a catchment area for local lab blood draws (i.e. central contracted laboratory).

Disease Characteristics

- Meet criteria for probable AD dementia according to the National Institute of Aging

 Alzheimer's Association (NIA-AA) 2018 core research criteria 109, and have the following at screening:
 - A diagnosis of mild AD or moderate AD, or
 - A provisional research diagnosis consistent with probable mild AD or moderate AD, and
 - MoCA score of 4-24 inclusive.
- Have positive biomarker for brain amyloid pathology as shown by:

- (Optional, per PI judgment for clarification on appropriateness for screening) Positive plasma assay for AD biomarkers (such as $A\beta(42)/A\beta(40)$ ratio or pTau217) AND/OR
- Either positive CSF assay for AD assessment (A β (1-42) is <1026 pg/mL, p-tau:A β (1-42) ratio is \geq 0.023) or positive amyloid PET, per PI read.
- 8 If receiving anti-dementia treatment (i.e., cholinesterase inhibitor and/or Memantine), be on stable treatment for at least 60 days before initial screening visit and up to the baseline visit.

Be stable on all other medications for at least 30 days prior to initial screening visit.

9 Have had a dental exam within 6 months of date of screening.

6.1.2 Exclusion Criteria

Individuals who meet any of the following criteria will be excluded from this study:

Exclusion Criteria

Participant Characteristics Exclusions

- 1 Individuals with a first degree relative diagnosed with AD before 55 years of age.
- **2** BMI ≥35.
- 3 Is unable to read/write at an appropriate level to reliably participate in clinical trial psychometric assessments.
- 4 Is a prisoner.

Medical Condition Exclusions

- Other neurological or psychiatric condition (other than AD) that can impact cognition, as well as atypical presentations of AD and AD related dementias, including logopenic primary progressive aphasia (PPA), or posterior cortical atrophy (PCA); or, CT/MRI evidence of potentially significant intracranial abnormalities not related to AD (e.g., evidence of major stroke or lacune in an area critical to cognition, infections, cancer, hydrocephalus, multiple sclerosis, etc.); or abnormal CSF not consistent with AD.
- Presence of current, serious mood or anxiety disorder, and/or a psychotic disorder, and/or a substance-related disorder according to Diagnostic and Statistical Manual of Psychiatric Disorders, Edition IV, text revision (DSM-IV-TR) or DSM-V that, in the opinion of the Principal Investigator, might impact cognitive assessment, affect participants ability to complete the study, or confound interpretation of the study drug effect; or is considered suicidal or shows suicidal ideation as assessed by the study physician, including, but not limited to:
 - Endorsing positive answer to C-SSRS suicidal ideation (items 4 or 5) or is positive for any suicidal behaviors within 6 months of screening, or has been hospitalized or treated for suicidal behaviors within past 5 years before screening.

- Severe depression as indicated by a GDS score of 20 or higher.
- Severe anxiety as indicated by a GAD-7 score of 15 or higher.
- Recent history (within 2 years of Screening) of alcohol or substance abuse or dependence, as determined by DSM-V criteria and in the judgement of the investigator.
- Positive urine drug panel (due to non-prescription drug) at Screening, or use of cannabinoids (prescription or recreational).
- History of unprovoked deep vein thrombosis, pulmonary embolism, familial predisposition for deep vein thrombosis, or pulmonary embolism, per study doctor judgement.
- 8 Active cancer / malignant neoplasm within 5 years of screening other than nonmelanoma skin cancers (e.g. Basal cell or squamous cell). Previous diagnosis of Leukemia, despite remission state or length of time, is considered exclusionary.
- 9 History of a latex or yeast allergy.
- Presence/history of drug hypersensitivity; or known hypersensitivity to sargramostim, yeast-derived products, any other component of the product, or benzyl alcohol (present in bacteriostatic water or saline for injection).
- History of asplenia, hyposplenia, or splenectomy (for any indication).
- History of, or treatment for, an autoimmune disease (e.g. Rheumatoid Arthritis, Multiple Sclerosis, Myasthenia Gravis, etc.).
- Untreated or unstable medical condition that could interfere with the study assessments in the opinion of the study physician, or may require use of excluded medications or treatments as specified in Appendix H.
- History of seizures (except infant febrile seizures).
- Pregnant or breastfeeding female, or female of childbearing potential and not protected by highly effective contraceptive method of birth control (i.e., oral or depot contraceptives or intrauterine device (IUD) or participant was surgically sterilized) and/or unwilling or unable to be tested for pregnancy; Male refusing to use condoms, if partner can get pregnant.

Lumbar Puncture, MRI, PET, Vital Signs, ECG, Laboratory Tests and Physical Examination Exclusions

- MRI evidence of >4 micro-hemorrhages; participants who may be prone to spontaneous ARIA-H and/or may be more susceptible to adverse effects of the ARIA-H.
- Laboratory results that are, in the judgement of the investigator, indicative of an untreated medical or hematologic condition that could increase risk or interfere with study assessments, including untreated hypo- or hyperthyroidism, vitamin B12

deficiency, hyperleukocytic syndrome (including, but not restricted to, chronic myelogenous leukemia, Hodgkin and non-Hodgkin lymphoma), monoclonal gammopathy, and/or thrombocythemia. (Regarding hematologic values, if screening ANC>70% or 7.7X10³/mm3 or WBC>11,500/mm³ and if this is sustained for > two weeks on recheck, a medical evaluation and clearance for underlying conditions, as well as return to normal prior limits, must be met prior to consideration for further enrollment procedures.)

18 Evidence of:

- Clinically significant pre-existing fluid retention (clinical or radiological);
- respiratory symptoms (e.g., dyspnea), moderate-to-severe lung disease (e.g. COPD, pulmonary infiltrates);
- cardiovascular symptoms or electrocardiographic evidence of cardiac disease that warrant therapeutic intervention (e.g., congestive heart failure, supraventricular arrhythmia, heart block, uncontrolled atrial fibrillation, etc.)
- a resting pulse less than 50, as reviewed by the study physician;
- prolonged QTc interval >470 ms in females, 450 ms in males).
- screening blood pressure measurement of greater than 160 systolic and/or 95 diastolic. If initial screening blood pressure is outside these parameters, BP will be taken in triplicate over the course of the visit with average BP to be evaluated by the delegated clinical sub-I.
- 19 Known renal dysfunction or serum creatinine >150 μmol/L, or Glomerular Filtration Rate (GFR) less than 55 ml/min.
- Known hepatic dysfunction (apart from Gilbert's syndrome) or serum ALT \geq 3 times the upper limit of normal (ULN).
- Positive serology for hepatitis B surface antigen (HBs Ag), anti-hepatitis C virus (anti-HCV), anti-human immunodeficiency virus 1 and 2 antibodies (anti-HIV1 and anti-HIV2 Ab) or spirochetal infection (e.g. syphilis).
- Contraindication or inability to complete magnetic resonance imaging (e.g., cardiac pacemaker/defibrillator, ferromagnetic metal implants) or PET scan.
- **24** Sensitivity to fluorodeoxyglucose F 18
- Having past or planned exposure to ionizing radiation that would, together with the radiation resulting from the administrations of the PET tracer(s) used in this study, exceed applicable institutional, local, or national recommendations for annual or lifetime exposure.
- 26 Poor venous access.
- 27 History of chronic or recurrent bacterial infections, at the discretion of the PI or delegated sub-I.

Prior / Concomitant Therapy Exclusions

Is taking any prohibited medication or therapy (see 7.7 Concomitant Therapy section and Appendix H).

Prior / Concurrent Clinical Trial Experience

- Be the recipient of an investigational drug within 60 days of screening, or within 5 times the elimination half-life of that drug, whichever is the longest.
- Prior treatment with an investigational anti-amyloid or anti-tauopathy therapy, or AD vaccine, unless it can be documented that they were on placebo.
- Participation in the treatment phase of an investigational sargramostim clinical trial within 6-months of screening.
- Have previously withdrawn from this study (This exclusion does not apply to participants who are eligible to rescreen before randomization in this study)

Other Exclusions

- 33 Any interested participant who:
 - a. Is in the judgement of the Principal Investigator likely to be non-compliant with study protocol, including, but not limited to, leaving the area of the study for any extended period; or separate from the designated caregiver/informant, without acceptable replacement, for any of the scheduled assessment visits during the study.
 - b. Is unable to cooperate because of a language problem or because of a developmental disability.
 - c. Oversees or implements any aspect of the study, or is employed by Partner Therapeutics or its affiliates or subsidiaries, or is an employee of the University of Colorado Alzheimer's and Cognition Center and is engaged in the conduct of the study, or first degree relative of such.
- Any technical/administrative reason that makes it impossible to randomize the participant in the study (e.g. kyphosis or other physical condition that prevents neuroimaging acquisition or other examinations, conflicts in participant schedules, etc.).

NOTE: Investigators will ensure that all study enrollment criteria have been met at screening. If a participant's status changes (including laboratory results or receipt of additional medical records) after screening but before the first dose of study drug is given such that he or she no longer meets all eligibility criteria, then the participant will be excluded from participation in the study.

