End of week relative to study randomization day ¹ :	Week -12 to Week -1
Tolerance Interval for Visit (in days) ¹	84
Screening Visit Procedures (By Tier)	
Tier 0.5	
Screening Procedures	
Mini Informed Consent	X
Demographics	X
Cognitive Health Review Battery ¹³	X
Optional blood draw for biomarker AD evaluation (such as $A\beta(42)/A\beta(40)$ ratio or	X
pTau 217 ¹⁴	
Tier 1	
Screening Procedures	
Full Informed consent (participant and study partner) ²	X
Demographics	X
Medical History	X
Previous / Concomitant Meds	X
Physical / Neurological Exam	X
Diagnostic assessment for mild-to-moderate AD (as necessary) ¹²	X
Screening Entry Diagnostics	
MoCA	X
Vital signs (i.e. BP, HR, Temperature, Respirations) ³	X
Height and Weight	X
ECG	X
GDS ⁴	X
GAD-7 ⁵	X
C-SSRS ⁶	X
Screening Laboratory Diagnostics	
Urinalysis	X
Prohibited drugs	X
Pregnancy (if applicable)	X
CBC+ Diff, CMP, PT/INR	X
Blood draw for counter-indicated conditions ⁷	X
Tier 2	
Screening Imaging Diagnostics	X 7
MRI Scan ⁸	X
Tier 3	
Screening Laboratory Diagnostics	**
Lumbar Puncture for Aβ CSF Assay (if selected for entry criteria) ⁹	X
Amyloid PET ¹⁰ (if selected for entry criteria)	X
Blood draw for serum/CSF Albumin index, CSF and Serum Glucose, CSF Protein	X
& Total cell count (if LP conducted) Vital signs prior to Lymbor Pyrottym (i.e. DP, HP, Tomorottym, Poprioritions) if	v
Vital signs prior to Lumbar Puncture (i.e. BP, HR, Temperature, Respirations) if LP conducted) ³	X

Review of NIA-AA Criteria	X
Review of Inclusion/Exclusion Criteria ¹¹	X
Tier 4 (Optional)	
Screening Laboratory and Imaging Diagnostics	
Amyloid PET ¹⁰ (if selected for optional substudy)	X
Lumbar Puncture for Aβ CSF Assay (if selected for optional substudy) ⁹	X

¹The interval between the screening visit and the baseline visit is a maximum of 84 days to allow for completion of all screening procedures, assessments and evaluations. The visit is not considered complete until all procedure to determine eligibility (Tiers 0.5-3) are completed and reviewed. Screening visit can take place over multiple days, with expectation that each separate Tier will be completed within a 1 day visit, with an expected 3 mandatory site visits and 1 optional visit.

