5.3.1 Screening Procedures

Screening procedures are listed below and shown in Schedule of Events section (Section 2). Assessments and procedures used throughout the study are described in more detail in Section 8. If any results of the screening procedures warrant concern for the participant's well-being and/or additional care, the participant will either be referred to their appropriate medical provider or if urgent, escorted or transferred to the Emergency Department for follow-up care.

All mandatory Tier 0.5 screening procedures and assessments must be completed and evaluated by the PI/sub-I before any Tier 1 procedures and assessments are initiated. All Tier 1 screening procedures and assessments must be completed and evaluated by the PI/sub-I before any Tier 2 procedures and assessments are initiated. Similarly, all Tier 2 assessments and procedures (Screening MRI) must be completed and evaluated by the PI/sub-I before any Tier 3 procedures (Screening LP or Screening Amyloid PET). The optional amyloid PET or optional LP substudy procedures (Tier 4) will be only be conducted after results of the Tier 3 entry criteria are evaluated and the participant meets inclusion/exclusion criteria.

• Tier 0.5

- Mini-Informed Consent
- Demographics
- Cognitive Health Review Battery*
 - *At study physician discretion, the cognitive health review battery can be minimized to included only the FAQ and DSRS based upon available medical history.
- Optional (per PI/sub-I discretion for clarity on eligibility for screening) Blood draw for screening biomarker for Alzheimer's disease, such as plasma $A\beta(42)/A\beta(40)$ ratio or pTau 217 may be conducted

Tier 1

- o Full Informed Consent
- Physical and neurological exam
- Montreal Cognitive Assessment (MoCA): After informed consent is obtained, the cognitive entry criteria, the MoCA, will be one of the first assessments or procedures, performed by a trained cognitive rater. Participants who do not meet the MoCA screening criteria are not to have any further screening procedures performed, and participants who qualify based on the MoCA entry criteria will then proceed to the remaining screening criteria.
- Medical history review
- o Previous and concomitant medications
- Vital signs (i.e. BP, HR, Temperature, Respirations) Blood pressure and pulse should be measured in the sitting position only. Refer to section 8.4.5.3 Data Monitoring Plan for acceptable BP parameters.
- Height and weight
- o ECG

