 - Generalized Anxiety Disorder (GAD)-7: The GAD-7 is a simple seven item questionnaire used to identify anxiety levels in individuals. The GAD-7 is calculated by assigning scores of 0, 1, 2, and 3, to the response categories of "not at all," "several days," "more than half the days," and "nearly every day," respectively. GAD-7 total score for the seven items ranges from 0 to 21. Scores of 5, 10, and 15 represent cutpoints for mild, moderate, and severe anxiety, respectively. Though designed primarily as a screening and severity measure for generalized anxiety disorder, the GAD-7 also has moderately good operating characteristics for three other common anxiety disorders: panic disorder, social anxiety disorder, and post-traumatic stress disorder.
- Screening Laboratory Assessments
 - Approximately 16 ml of blood will be drawn for a CBC with differential and CMP, PT INR, and for serology evaluation of treponema, HBsAg and anti-HCV, anti-HIV1, and anti-HIV2 antibodies.
 - The creatinine level from the CMP will be used to calculate the estimated GFR to assess kidney function if not provided by the central laboratory.
 - Urine for exclusionary substances.
 - For women who cannot confirm they are post-menopausal per clinician satisfaction, a urine pregnancy test will be performed.

• Tier 2

Screening MRI: A screening MRI will be performed as part of eligibility to assess for evidence of prior or existing neurological disease (e.g. stroke, microhemorrhage, cancer, etc.), to exclude other potential causes of dementia, and to assess for MTA. Aside from the Tier 3 procedure, the participant should have met all other screening inclusion criteria before the MRI is performed. The MRI scan will be reviewed by a Radiologist and then results and/or the scan will be reviewed by the Principal Investigator to determine eligibility. The PI will share any medically relevant information that might indicate a health risk with the participant and LAR that is in the MRI report.

Tier 3

0

o Participant may choose either as entry criteria to confirm plasma $A\beta(42)/A\beta(40)$ ratio from Tier .5

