■ Screening Lumbar Puncture (LP) for CSF Assay: A lumbar puncture (LP) will be performed to obtain cerebrospinal fluid (CSF) and each participant's amyloid status will be evaluated at a central screening laboratory via CSF A β 1-42 and p-tau:A β (1-42) ratios using validated assay methods demonstrating high sensitivity and specificity (e.g. Athena Diagnostics; ADmark® Phospho-Tau/Total-Tau/A Beta42). These assays will be performed at a central laboratory (i.e. Athena Diagnostics) with the p-tau:A β (1-42) ratio results being reported to the investigator for eligibility determination. The accepted reference values in non-AD individuals is A β (1-42) >1026 pg/mL and p-tau/A β (1-42) ratio ≤0.023. For inclusion criteria consistent with the presence of pathological changes associated with AD, the values for A β (1-42) should be <1026 pg/mL and the values for p-tau/A β (1-42) ratio ≥0.023. CSF will also be assessed for glucose and protein levels to ensure safety.

- Additionally at this Tier 3 visit, approximately 4ml of blood will be drawn at the same visit to be used in conjunction with the CSF to quantitate both serum and CSF albumin levels and calculate an albumin index (AI) for assessment of AD-related permeability changes in the blood brain barrier ¹⁰⁸.
 - CSF total protein
 - CSF Total cell count
 - CSF and serum glucose
 - Extra CSF sample that is not used for these assays will be aliquoted and stored for biomarker assays (e.g. 5.3.1.1 below), which are dependent on the participant meeting all inclusion criteria and being enrolled into the trial. If the participant does not enroll into the trial, the extra CSF samples will be removed from storage, discarded, and not used for any biomarker assays, unless the participant consents for these samples to be banked and used in further research studies.
 - It is anticipated that results of the CSF assay will be available within the 84 day screening period. However, it will not be considered a protocol violation should the assay results not be available until after the 84 day screening period has concluded. It will be allowable for the screening period to be extended if the CSF assay results are not available within the 84 day screening window.
 - Vital signs including BP, pulse, respirations, and temperature will be collected prior to the LP procedure, if performed.

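### Exclusion 17 names thyroid disease, vitamin B12 deficiency and monoclonal gammopathy, but no listed screening draw measures them, so undiagnosed or undocumented cases can pass screening

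*Protocol*

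**What the plan says.** Exclusion 17 (Protocol section 6.1.2, in the block of procedure, laboratory and examination exclusions) is triggered by "Laboratory results that are, in the judgement of the investigator, indicative of an untreated medical or hematologic condition that could increase risk" or interfere with the study assessments. Its examples are "including untreated hypo- or hyperthyroidism, vitamin B12" deficiency, hyperleukocytic syndrome, and "monoclonal gammopathy, and/or thrombocythemia". For neutrophil and white cell counts it adds numerical limits and a recheck rule.

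The Tier 1 laboratory rows of the screening schedule (section 2) give "CBC+ Diff, CMP, PT/INR", urinalysis, a prohibited-drug test, a pregnancy test if applicable, and a draw for contraindicated conditions. Footnote 7 limits that last draw to hepatitis B, hepatitis C, HIV and syphilis. Section 5.3.1 itemises the same content: "Approximately 16 ml of blood will be drawn for a CBC with differential and CMP, PT INR, and for serology evaluation of treponema", hepatitis B and C, and HIV. At Tier 3, if a lumbar puncture is chosen, blood is also taken to "quantitate both serum and CSF albumin levels and calculate an albumin index (AI"), together with glucose.

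Tier 1 also contains "Medical history review", concomitant medications, and a physical and neurological examination.

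**The concern.** A criterion based on laboratory results works only if a result exists. For three of the conditions named in exclusion 17, the protocol neither orders a test nor asks for a previous one. The criterion then reaches people whose disease someone has already recorded, and misses people whose disease is untreated because nobody has found it.

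The protocol's own wording says what is at stake: these are conditions it regards as possibly raising risk or disturbing the assessments. The closing note of section 6.1.2 makes investigators responsible for seeing that every enrolment criterion is met at screening. For these three conditions they may have nothing to check against, and the criterion may be applied differently from one participant to the next, depending on what outside records happen to be available.

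**Working it through.** No arithmetic beyond a count applies, and the plan gives no figure to reproduce. The check sets each condition named in exclusion 17 against every screening laboratory list in the protocol.

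| Condition named in exclusion 17 | Screening test listed? |
|---|---|
| Hypo- or hyperthyroidism, untreated | None |
| Vitamin B12 deficiency | None |
| Hyperleukocytic syndrome | Yes: CBC with differential |
| Monoclonal gammopathy | None |
| Thrombocythemia | Yes: CBC (platelets) |

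Five conditions are named and two are covered, so 5 − 2 = 3 are not. The lists compared were the Tier 0.5 to Tier 4 schedule with its footnotes (section 2), the screening laboratory assessments and the Tier 3 draw (section 5.3.1), the additional screening considerations (section 5.3.2) and the laboratory section (8.2). The protocol does not itemise the CMP. I assume that it is the usual metabolic panel, without a thyroid, B12 or paraprotein assay; it and the CBC could then give at most an indirect hint.

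Next, is an earlier result required from elsewhere?

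- No inclusion or exclusion criterion asks for a prior thyroid, B12 or paraprotein result. The protocol does set an outside requirement of this kind when it wants one: inclusion 9 asks for a dental examination within 6 months of screening.
- The note closing section 6.1.2 lets new laboratory results or medical records exclude a participant before the first dose. It does not oblige anyone to obtain them.
- A prior dementia work-up is not assured. Section 5.2 recruits from the community as well as the memory clinic. Section 5.3.1 allows someone with a confirmed diagnosis of only mild cognitive impairment to enter on a provisional research diagnosis, made by interview, functional scales and agreement with a second study doctor; that assessment includes no blood test.

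Finally, comparison with the neighbouring criteria. The creatinine and GFR limit and the ALT limit can be read from the CMP, and the infection exclusion matches the serology draw. The three conditions above lack such a counterpart.

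**The case against.** The strongest reply is that exclusion 17 promises no dedicated assays. It is a judgement criterion, its conditions are examples, and it does not say that the results must come from the trial's own draws. Untreated is also not the same as undiagnosed: someone with documented but untreated hypothyroidism falls squarely within it. History, medications and examination are reviewed in Tier 1, criterion 13 separately excludes untreated or unstable conditions without needing a laboratory result, and outside records can exclude up to the first dose. All of this stands, and it limits the point to undiagnosed or undocumented cases. A reader might infer that people with these conditions simply pass screening; the documents do not support that.

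It can also be said that the Manual of Procedures, which is not at hand, may describe how outside results are gathered. Section 5.3.2 does refer to it for details of the eligibility review. That possibility remains open, but the protocol's screening laboratory lists do not point there for further tests. The Tier 0.5 questionnaire battery is meant to pick up mimics of Alzheimer's disease, but it contains no blood test and may be shortened to two functional scales.

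A reader might further infer that the MMSE comparison would be biased. The documents do not support this either. They give no prevalence for these conditions and no size for their effect on the MMSE, and under randomisation such cases would be expected to add noise rather than favour one arm.

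**Conclusion.** The point holds in limited form. Exclusion 17 names three conditions that no listed screening draw measures and for which no earlier result is required, so undiagnosed or undocumented cases can be randomised with the plan followed exactly. Documented cases remain excludable.

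The size is three of five named conditions. How many participants this would involve cannot be derived from the documents. The conclusion rests on the CMP being a usual metabolic panel and on the Manual of Procedures not adding screening tests. It is a cheap improvement of minor severity: it concerns whether an eligibility criterion can be applied and audited, and it is not a demonstrated threat to the trial's safety or efficacy conclusions.

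Nor does it follow that the three conditions should be struck from the criterion. That would remove an exclusion that still works for documented cases.

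**What to change.** Bring exclusion 17 and the Tier 1 laboratory list into agreement by one of two routes, and use the same wording in section 2, section 5.3.1 and section 6.1.2:

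- add assays corresponding to the three conditions to the existing Tier 1 blood draw; or
- require a documented result for each, dated within a period before screening that the sponsor sets, and state that exclusion 17 is judged on it.

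Keep the named conditions in either case. The cost is an amendment to the text and either additional assays on a draw already taken or a record check, with a small rise in screening cost and screen failures. If assays are added, the laboratory should confirm whether the stated volume of about 16 ml is still enough.
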